## **7.2. Method of Treatment Assignment**

Participants eligible to enter the study will be assigned to treatment randomly via an interactive response technology (IRT) system. The randomization schedule will be generated using the GSK validated randomization software RandAll NG. The study will be randomized separately for each country. Participants will be assigned to study treatment in accordance with the randomisation schedule. Once a randomization number has been assigned to a participant, it cannot be reassigned to any other participant in the study.

Study treatment will be dispensed at the study visits summarized in SoA

Returned study treatment should not be re-dispensed to the participants.

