#### 10.3.1. Efficacy Analyses

Endpoint	Statistical Analysis Methods
Co-Primaries	
Total endoscopic nasal polyp score is collected at each clinical visit, the primary assessment will be at week 52 (centrally read data). Nasal obstruction is collected daily throughout the study via eDiary. Nasal obstruction at Week 52 will be calculated as the mean of all measurements made in the 4 weeks prior to the visit (excluding the day of the visit). The mean VAS score over the last 7 days before Visit 2 will be used to determine the baseline value.
 
Participants who undergo surgery/sinuplasty prior to Week 52 will be assigned their worst observed value prior to surgery/sinuplasty. Participants who withdraw from study without having experienced surgery/sinuplasty will be assigned their

Endpoint	Statistical Analysis Methods
	
worst observed score prior to study withdrawal.
 
The comparison of mepolizumab with placebo will be expressed as a difference in median change from baseline presented with corresponding 95% confidence intervals, the p-value for the difference between treatment groups will be based on the non-parametric Wilcoxon rank-sum test. The difference in median change between placebo and mepolizumab with associated 95% confidence intervals will be assessed by quantile regression using a bootstrap approach (Mehrotra DV 2017; Keene O.N 2018), with covariates of treatment group, baseline score, baseline blood eosinophil count and region.

Secondary	
Time to actual NP surgery will be compared between treatment groups using a Cox's proportional hazards model with covariates of treatment group, baseline NP score, baseline nasal obstruction score and region. Graphs of the Kaplan-Meier estimates of the proportion of participants with events over time will be produced by treatment group.
 
Change from baseline in mean overall VAS symptom score, mean composite VAS score (combining VAS scores for nasal obstruction, nasal discharge, mucus in the throat and loss of smell) and mean VAS loss of smell score at Week 52 (calculated as the mean of all measurements made in the 4 weeks prior to Week 52), and change from baseline in SNOT-22 total score at Week 52 will be analysed in a similar manner to the co-primary endpoints. The proportion of participants requiring systemic steroids for nasal polyps will be analysed using a logistic regression model.

"other"	Will be described in the reporting and analysis plan

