Treatment Assignment	
 400 participants (planned) will be randomised in a 1:1 ratio to receive mepolizumab or matching placebo (i.e. 200 per treatment group) delivered subcutaneously via a pre-filled safety syringe in addition to SoC. Randomisation schedule generated using GSK validated randomisation software RandAll NG, stratified by country. Treatment assigned randomly via an interactive voice response system (IVRS).
Interim Analysis	
 No interim analysis of data is planned for this study.

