5.5. Multiple Comparisons and Multiplicity

The treatment comparison of mepolizumab 100mg SC vs. placebo is of interest for the co-primary and secondary endpoints. Multiplicity arising from the multiple secondary endpoints will be controlled through testing of the secondary endpoints using a closed testing procedure according to the following pre-defined hierarchy:

1. Time to first nasal surgery
2. Change from baseline in overall VAS symptom score
3. Change from baseline in SNOT-22 total score
4. Proportion of subjects requiring systemic steroids for nasal polyps
5. Change from baseline in the mean composite VAS score (nasal obstruction, nasal discharge, mucus in the throat and loss of smell)
6. Change from baseline in mean individual VAS symptom score for loss of smell

For strong control of type I error, statistical significance for the first secondary endpoint in the pre-defined hierarchy will be dependent on statistical significance having been achieved for the two co-primary endpoints. Statistical significance for the subsequent secondary endpoints will be dependent on statistical significance having been achieved for the previous endpoints in the hierarchy.

For secondary endpoints, unadjusted p-values and p-values adjusted for multiplicity based on the above hierarchy, will be presented.

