7.2.1.4. Statistical Analyses / Methods

Endpoint / Variables					

 Time to first nasal surgery 					
Model Specification					

 Cox proportional hazards model with covariates as follows: 
 
 Fixed Categorical:	Treatment group, Region	
 
 Fixed Continuous:	Baseline total nasal polyps endoscopic score (centrally read data), Baseline nasal obstruction VAS, Log_e baseline blood eosinophil	
 
 		Fixed Categorical:	Treatment group, Region	Fixed Continuous:	Baseline total nasal polyps endoscopic score (centrally read data), Baseline nasal obstruction VAS, Log _e baseline blood eosinophil
Fixed Categorical:	Treatment group, Region				
Fixed Continuous:	Baseline total nasal polyps endoscopic score (centrally read data), Baseline nasal obstruction VAS, Log _e baseline blood eosinophil				

	count, Number of previous surgeries (1, 2, >2; ordinal)

 Participants with missing covariate information will be excluded from the analysis 	
Model Checking & Diagnostics	

 A log(-log(survival)) plot by treatment group will be used to assess the assumption of proportional hazards. 	
Model Results Presentation	

 The number of participants with an event, the number censored due to study withdrawal and at study completion will be presented by treatment arm. The hazard ratio with corresponding 95% CI and p-value from the Cox proportional hazards model will be presented. A summary and graph of the Kaplan-Meier estimate of the cumulative proportion of participants with nasal surgery within each treatment arm over time will be produced. 	
Subgroup Analyses	

 No subgroup analyses are planned for this endpoint. 	
Sensitivity and Supportive Analyses	

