
 For each endpoint the p-value for the difference in median change from baseline between treatments will be based on the non-parametric Wilcoxon rank-sum test. The difference in median change from baseline with 95% confidence intervals will be estimated by quantile regression using a bootstrap approach. The analysis model will include the following terms: 
 
 Fixed Categorical:	Treatment group, Region	
 
 Fixed Continuous:	Baseline score, Log_e baseline blood eosinophil count	
 
 
 Participants with missing covariate information will be excluded from the analysis 	Fixed Categorical:	Treatment group, Region	Fixed Continuous:	Baseline score, Log _e baseline blood eosinophil count
Fixed Categorical:	Treatment group, Region			
Fixed Continuous:	Baseline score, Log _e baseline blood eosinophil count			
Model Checking & Diagnostics				

 Models will be checked for issues with convergence. 				
Model Results Presentation				

 Median change from baseline within each treatment group. Estimated difference between treatments in median change from baseline with 95% confidence interval (CI). p-value comparing treatment groups from the Wilcoxon rank-sum test. 				
Subgroup Analyses				

 No subgroup analyses are planned for this endpoint 				
Sensitivity and Supportive Analyses				

 No sensitivity/supportive analyses are planned for these endpoints 				

7.2.3. Change from Baseline in Sino-Nasal Outcomes TEST 22 (SNOT-22) Total Score at Week 52

The 22 questions of the SNOT-22 are each graded on a

CCI - This section contained Clinical Outcome Assessment data collection questionnaires or indices, which are protected by third party copyright laws and therefore have been excluded.

Details regarding the summary measure, population of interest and the strategy for intercurrent events are provided in Section 7.1.2 to Section 7.1.4.

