7.2.3.1. Statistical Analyses / Methods

Endpoint / Variables

 Change from baseline in SNOT-22 total score at Week 52

Model Specification					

 The p-value for the difference in median change from baseline between treatments will be based on the non-parametric Wilcoxon rank-sum test. The difference in median change from baseline with 95% confidence intervals will be estimated by quantile regression using a bootstrap approach. The analysis model will include the following terms: 
 
 Fixed Categorical:	Treatment group, Region	
 
 Fixed Continuous:	Baseline score, Log_e baseline blood eosinophil count	
 
 
 Participants with missing covariate information will be excluded from the analysis 		Fixed Categorical:	Treatment group, Region	Fixed Continuous:	Baseline score, Log _e baseline blood eosinophil count
Fixed Categorical:	Treatment group, Region				
Fixed Continuous:	Baseline score, Log _e baseline blood eosinophil count				
Model Checking & Diagnostics					

 Models will be checked for issues with convergence. 					
Model Results Presentation					

 Median change from baseline within each treatment group. Estimated difference between treatments in median change from baseline with 95% confidence interval (CI). p-value comparing treatment groups from the Wilcoxon rank-sum test. 					
Subgroup Analyses					

 No subgroup analyses are planned for this endpoint. 					
Sensitivity and Supportive Analyses					

 No sensitivity/supportive analyses are planned for this endpoint. 					

7.2.4. Proportion of subjects requiring systemic steroids for nasal polyps up to Week 52

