7.2.4.4. Statistical Analyses / Methods

Endpoint / Variables					

 The proportion of subjects requiring at least one course of systemic steroids for nasal polyps up to Week 52 					
Model Specification					

 A logistic regression model will be used to compare the proportion of participants requiring a course of systemic steroids up to week 52 in the mepolizumab arm compared to placebo. The odds ratio comparing treatment groups will be estimated using the observed marginal distribution of the sample covariates. The analysis model will include the following terms: 
 
 Fixed Categorical:	Treatment group, Region	
 
 Fixed Continuous:	Number of OCS courses for NP in last 12 months (0, 1, >1; ordinal), baseline total endoscopic NP score (based on centrally read data), baseline nasal obstruction VAS score, Log_e baseline blood eosinophil	
 
 		Fixed Categorical:	Treatment group, Region	Fixed Continuous:	Number of OCS courses for NP in last 12 months (0, 1, >1; ordinal), baseline total endoscopic NP score (based on centrally read data), baseline nasal obstruction VAS score, Log _e baseline blood eosinophil
Fixed Categorical:	Treatment group, Region				
Fixed Continuous:	Number of OCS courses for NP in last 12 months (0, 1, >1; ordinal), baseline total endoscopic NP score (based on centrally read data), baseline nasal obstruction VAS score, Log _e baseline blood eosinophil				

 Participants with missing covariate information will be excluded from the analysis 					
Model Checking & Diagnostics					

 Models will be checked for issues with convergence 					
Model Results Presentation					

 The number and percentage of participants identified as requiring at least one course of systemic steroids for nasal polyps will be displayed by treatment group, as will the number of courses of therapy required. The estimated odds ratio, 95% CI and p-value comparing treatments from the logistic regression model will be displayed. 					
Subgroup Analyses					

 No subgroup analyses are planned for this endpoint. 					
Sensitivity and Supportive Analyses					

 No sensitivity/supportive analyses are planned for this endpoint. 					

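### Optional improvement, not an error: four secondary endpoints take the p-value that drives the fixed sequence from an unadjusted Wilcoxon test, although the plan already uses suitable covariates for their confidence intervals

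*SAP*

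**What the plan says.** Protocol 10.3.1 says that the three VAS secondaries and SNOT-22 "will be analysed in a similar manner to the co-primary endpoints". The SAP carries this out in two parts. For overall VAS, composite VAS and loss of smell (SAP 7.2.2.1), "the p-value for the difference in median change from baseline between treatments will be based on the non-parametric Wilcoxon rank-sum test", and SAP 7.2.3.1 repeats it for SNOT-22: "The p-value for the difference in median change from baseline between treatments will be based on the non-parametric Wilcoxon rank-sum test". No stratum or covariate is named for the test. The median difference and its 95% interval come from a bootstrapped quantile regression with treatment, region, baseline score and log baseline eosinophils.

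The other two secondaries are tested in adjusted models. For surgery, SAP 7.2.1.4 has a "Cox proportional hazards model with covariates as follows"; for steroid use, SAP 7.2.4.4 says "A logistic regression model will be used to compare the proportion of participants requiring a course of systemic steroids up to week 52", again with covariates.

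SAP 5.5 sets the order: surgery, overall VAS, SNOT-22, steroid use, composite VAS, loss of smell. "Statistical significance for the subsequent secondary endpoints will be dependent on statistical significance having been achieved for the previous endpoints in the hierarchy". Protocol 7.2 says "The study will be randomized separately for each country". No sensitivity or supportive analysis is planned for the four rank-tested secondaries.

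**The concern.** The sponsor evidently regards region, baseline score and eosinophils as useful for these endpoints, since they adjust the interval. They do not adjust the p-value, and the p-value decides whether testing continues. If overall VAS is missed, the four endpoints after it lose formal testing; if SNOT-22 is missed, the three after it do. Protocol 10.1 states power only for the co-primaries and surgery, so no figure shows how much room these four have. Adjusting the test would use data already collected. With no supportive analysis planned, the report would not show what an adjusted test gives.

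**Working it through.** **1. The plan's own figure.** Inputs from Protocol 10 and 10.1: 200 per arm, two-sided 5%, surgery 40% versus 25%. Power for two proportions: (0.15 − 1.96·√(2·0.325·0.675/200)) / √((0.40·0.60 + 0.25·0.75)/200) = (0.15 − 0.0918)/0.0462 = 1.26, giving 89.6%. By Schoenfeld, HR = ln 0.75/ln 0.60 = 0.563 with 80 + 50 = 130 events gives 90.5%. The stated 90% reproduces. The proportions formula gives 99.9% for NP score (27% versus 52%) and above 99.99% for nasal blockage (39% versus 70%).

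**2. Effect sizes implied by Phase II** (Protocol 1 and 3.1; arms of 54 and 51, so √(1/54 + 1/51) = 0.195):
- Overall VAS: −1.78 (−2.88, −0.68), SE = 2.20/3.92 = 0.561, SD = 0.561/0.195 = 2.87, d = 1.78/2.87 = 0.62. This was the per-protocol population, whose size is not given, so the SD is approximate.
- Individual VAS items, including loss of smell: p ≤ 0.002 implies d ≥ 3.09 × 0.195 = 0.60.
- SNOT-22: reported only as significant, which implies d ≥ 1.96 × 0.195 = 0.38. This is a floor, not an estimate.

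**3. Power with and without adjustment.** Power = Φ(d·√((3/π)·(n/2)/(1 − R²)) − 1.96), n = 200 per arm. R² is an assumption: two independent covariates, each correlated 0, 0.2 or 0.3 with outcome, give R² = 0, 0.08 or 0.18. The value d = 0.332 is a reference point chosen to give about 90% plain power; it is not taken from the documents.

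| d | R² = 0 (plain) | R² = 0.08 | R² = 0.18 |
|---|---|---|---|
| 0.332 | 90.0% | 92.3% | 94.8% |
| 0.383 (SNOT-22 floor) | 96.3% | 97.4% | 98.5% |
| 0.60 (VAS floor) | >99.9% | >99.9% | >99.9% |

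At half the Phase II overall VAS effect (0.89, SD 2.87), plain power is 85.7%, rising to 89.1% at R² = 0.10 and 92.3% at R² = 0.20.

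**4. Simulation of the trial's structure.** Assumed: 400 participants in the 11 countries of SAP 5.3, assumed country sizes, blocks of 4 within country, normal outcome. Rank ANCOVA with the SAP's region term and two covariates raised power from 90.4% to 92.8% and from 90.7% to 95.8% in two settings at d = 0.332, and from 96.3% to 97.5% at d = 0.383. With non-prognostic covariates it lost about 0.2 points. Its size was at or below 5%.

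**5. Country versus region.** With country explaining 5% of variance:

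| Setting | Plain | Country only | Region + covariates | Country + covariates |
|---|---|---|---|---|
| d = 0.332, correlation 0.3 | 90.6% | 91.6% | 95.6% | 95.9% |
| d = 0.383, correlation 0.2 | 96.4% | 96.8% | 97.4% | 97.7% |

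Replacing region with country adds 0.3 points in each row. The size of the plain test was 4.7–5.1% when country had no effect and 3.7–4.2% when country explained 10% of variance.

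**6. Cost of missing covariates.** Replacing n by 200·(1 − f) at d = 0.332 costs 0.6 points at f = 2%, 1.5 at 5% and 3.2 at 10%. The gain is cancelled when f reaches R².

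**The case against.** The strongest objection is that little is at stake on effects the documents support. At the VAS floor the gain is nil, and at the SNOT-22 floor plain power is already about 96%. That floor would rise if fewer than all 105 Phase II patients contributed. The larger gains need an effect and correlations that no section gives. Randomisation criterion 2 (Protocol 6.3) requires mean overall VAS above 7, which narrows the baseline range and may weaken it as a predictor for that endpoint. All of this stands. Against it, the Phase II results come from 750 mg IV at Week 25, so the effect of 100 mg SC at Week 52 could be smaller.

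A second objection is that sharing the co-primary method is deliberate. SAP 7.2.2 ties the VAS secondaries to nasal obstruction, and the Protocol Amendment 04 entry for Section 10.3.1, which covers both co-primary and secondary methods, cites regulatory feedback. With the change, nasal obstruction would be tested by Wilcoxon and the composite containing it by rank ANCOVA. This also stands and is the main cost.

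A reader might infer more: that ignoring country in the test, after randomising by country, makes it invalid. It does not. The omission makes the test slightly conservative if country predicts outcome. Nor is there a case for putting country groups into the models: region captures nearly all the gain, and SAP 5.3 already anticipates convergence trouble with three regions.

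**Conclusion.** The description of the plan is right, and the point is a modest improvement to consider. The Wilcoxon test is valid for all four endpoints. Adjusting it for region, baseline score and log eosinophils would add about 0 to 5 points of power where plain power is about 90%, about 0 to 2.4 points at the SNOT-22 floor, and nothing at the observed Phase II VAS effects. Nearly all of this comes from the baseline covariates. The range rests on assumed correlations, country sizes and block size. Confidence is moderate, because the prognostic value of the covariates is unknown.

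A reader might extend the point to the co-primaries. The documents do not support that: at the planning rates in Protocol 10.1 their power is already 99.9% or more.

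One matter needs clarifying whatever is decided. SAP 7.2.2.1 and 7.2.3.1 exclude participants with missing covariates without saying whether this covers the Wilcoxon test or only the quantile regression. If only the latter, p-value and interval may rest on different participants.

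**What to change.** Before unblinding, amend SAP 7.2.2.1 and 7.2.3.1, the linking sentence in SAP 7.2.2, and the matching sentence in Protocol 10.3.1. Take the p-value for the four endpoints from a rank ANCOVA: a linear model on the pooled ranks of the change score, with treatment, region, baseline score and log baseline eosinophils. Show the plain Wilcoxon p-value on all ITT participants as supportive. Leave the co-primary test and the quantile regression terms as they are. State whether the missing-covariate exclusion applies to the test, and report the number excluded by arm.

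No new data are needed. There are two costs. Participants with missing covariates may leave the test; this should be few, because a missing baseline score already removes the change score (SAP 14.6.4) and baseline eosinophils may come from any pre-dose sample (SAP 5.2.1). The secondary test would also differ from the co-primary method and may need re-agreement with the authority.

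If that is not wanted, keep Wilcoxon in the sequence and pre-specify the rank ANCOVA as a supportive analysis for these four endpoints. That needs SAP wording only.

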7.2.3.1. Statistical Analyses / Methods

Endpoint / Variables

 Change from baseline in SNOT-22 total score at Week 52

Model Specification					

 The p-value for the difference in median change from baseline between treatments will be based on the non-parametric Wilcoxon rank-sum test. The difference in median change from baseline with 95% confidence intervals will be estimated by quantile regression using a bootstrap approach. The analysis model will include the following terms: 
 
 Fixed Categorical:	Treatment group, Region	
 
 Fixed Continuous:	Baseline score, Log_e baseline blood eosinophil count	
 
 
 Participants with missing covariate information will be excluded from the analysis 		Fixed Categorical:	Treatment group, Region	Fixed Continuous:	Baseline score, Log _e baseline blood eosinophil count
Fixed Categorical:	Treatment group, Region				
Fixed Continuous:	Baseline score, Log _e baseline blood eosinophil count				
Model Checking & Diagnostics					

 Models will be checked for issues with convergence. 					
Model Results Presentation					

 Median change from baseline within each treatment group. Estimated difference between treatments in median change from baseline with 95% confidence interval (CI). p-value comparing treatment groups from the Wilcoxon rank-sum test. 					
Subgroup Analyses					

 No subgroup analyses are planned for this endpoint. 					
Sensitivity and Supportive Analyses					

 No sensitivity/supportive analyses are planned for this endpoint. 					

7.2.4. Proportion of subjects requiring systemic steroids for nasal polyps up to Week 52

7.2.4.1. Summary Measure

The summary measure of treatment effect will be the odds ratio which represents the relative odds of a participant requiring at least one course of systemic steroids up to Week 52 in the mepolizumab arm compared with placebo.

7.2.4.2. Population of Interest

The population of interest is the ITT population.

7.2.4.3. Strategy for Intercurrent (Post-Randomization) Events

Data will be included regardless of the occurrence of events such as surgery or treatment discontinuation.

7.2.4.4. Statistical Analyses / Methods

Endpoint / Variables					

 The proportion of subjects requiring at least one course of systemic steroids for nasal polyps up to Week 52 					
Model Specification					

 A logistic regression model will be used to compare the proportion of participants requiring a course of systemic steroids up to week 52 in the mepolizumab arm compared to placebo. The odds ratio comparing treatment groups will be estimated using the observed marginal distribution of the sample covariates. The analysis model will include the following terms: 
 
 Fixed Categorical:	Treatment group, Region	
 
 Fixed Continuous:	Number of OCS courses for NP in last 12 months (0, 1, >1; ordinal), baseline total endoscopic NP score (based on centrally read data), baseline nasal obstruction VAS score, Log_e baseline blood eosinophil	
 
 		Fixed Categorical:	Treatment group, Region	Fixed Continuous:	Number of OCS courses for NP in last 12 months (0, 1, >1; ordinal), baseline total endoscopic NP score (based on centrally read data), baseline nasal obstruction VAS score, Log _e baseline blood eosinophil
Fixed Categorical:	Treatment group, Region				
Fixed Continuous:	Number of OCS courses for NP in last 12 months (0, 1, >1; ordinal), baseline total endoscopic NP score (based on centrally read data), baseline nasal obstruction VAS score, Log _e baseline blood eosinophil				

 Participants with missing covariate information will be excluded from the analysis 					
Model Checking & Diagnostics					

 Models will be checked for issues with convergence 					
Model Results Presentation					

 The number and percentage of participants identified as requiring at least one course of systemic steroids for nasal polyps will be displayed by treatment group, as will the number of courses of therapy required. The estimated odds ratio, 95% CI and p-value comparing treatments from the logistic regression model will be displayed. 					
Subgroup Analyses					

 No subgroup analyses are planned for this endpoint. 					
Sensitivity and Supportive Analyses					

 No sensitivity/supportive analyses are planned for this endpoint. 					

